## **RISK/BENEFIT ASSESSMENT:**

## **1. Risks:**

Potential risks to participating in this study are minimal and primarily include potential violation of confidentiality or privacy.

## **2. Benefits:**

There are no direct benefits to participating in this study. If successful, this approach will be used to identify and enroll patients likely to be eligible for LCS in trials seeking to increase LCS through patient outreach. This approach will also be disseminated to other systems looking to increase uptake and equity of LCS in routine practice, adding to potential societal benefits.

## **3. Subject Privacy:**

Being asked to disclose information about smoking history could be viewed by some patients as a violation of privacy. As such, no patient will be required or forced to answer questions to ensure subject privacy is protected.

## **4. Subject Confidentiality:**

**How will confidentiality of data be maintained? Check all that apply.**

- Paper-based records will be kept in a secure location and only be accessible to personnel involved in the study.
- Computer-based files will only be made available to personnel involved in the study through the use of access privileges and passwords.
- Prior to access to any study-related information, personnel will be required to sign statements agreeing to protect the security and confidentiality of identifiable information.
- Whenever feasible, identifiers will be removed from study-related information.
- A Certificate of Confidentiality will be obtained because the research could place the subject at risk of criminal or civil liability or cause damage to the subject's financial standing, employability, or liability.
- A waiver of documentation of consent is being requested because the only link between the subject and the study would be the consent document and the primary risk is a breach of confidentiality. (This is not an option for FDA-regulated research.)
- Precautions are in place to ensure the data is secure by using passwords and encryption, because the research involves web-based surveys.
- Audio and/or video recordings will be transcribed and then destroyed to eliminate audible identification of subjects.
- Other (specify):

No identifying information will be shared outside of the study team, unless mandated by federal or state law. All identifying information will be removed from the analytic data set prior to analysis. Data will be securely retained and managed by the PI to support manuscripts, analysis, or future research after study completion. However, any use of data for future research outside of the scope of this study will be reviewed by IRB prior to use. Potential future research may include for example use of data for recruiting participants for studies related to LCS.

## **5. Protected Health Information**

For recruitment purposes, the following protected health information (PHI) will be requested from the Penn EHR:

- Name, address, phone, email (for recruitment purposes)
- All elements of dates
- Medical record numbers

We are requesting dates to be able to correctly determine age and years smoked at the time of recruitment. We are also requesting medical record numbers (MRNs) to be able to track participants longitudinally to assess LCS uptake in eligible patients. Prior to analysis, the PI will transform PHI data into deidentified variables (e.g., date will be transformed into length of time from index date, and MRNs will be transformed into a unique study ID). Once deidentified, the PI will remove all PHI from the analytic dataset.

## **6. Compensation:**

As part of our plan to test the impact of different message content on survey response, we will randomize approximately one-half of participants to be offered an incentive to complete the survey. Of these, the first 1,000 participants who complete the survey will be entered to randomly win one of 100 \$50 gift cards (delivered using Clincards). All other participants will not be offered compensation for completing the survey.

**7. Data and Safety Monitoring:** As a minimal risk study, data and safety will be monitored on an ongoing basis by the PIs and the study team. If an adverse event or data breach is reported, the PI in collaboration with [name] and [name] will evaluate the grade and relationship to the study and ensure appropriate course of action is taken and documented. The PI is ultimately responsible for reporting to the IRB and other regulatory bodies as required by Penn policies.

**8. Investigator's Risk/Benefit Assessment:**

The potential benefits of this study are great and include providing necessary data to understand rates of LCS in our patient population and support future studies looking to increase uptake in patients who are eligible for LCS. Given the very low rate of uptake of LCS at Penn and nationally, if proven to be successful, this study could have a significant positive impact on preventive care across healthcare systems. These potential benefits outweigh the very minimal risks, which include potential loss of privacy and confidentiality. Given the potential benefits and included protections against risk, the risks of participation do not exceed the potential benefit.

**INFORMED CONSENT:**

**1. Consent Process:**

Because this study is a nudge study that will be utilizing text message to deliver the survey, we are requesting a waiver of consent. This is justified because the recruitment involves no more than minimal risk to the subjects. The waiver will not adversely affect the rights and welfare of participants as the data are being collected as part of routine care, and care will not be directly impacted based on analysis. Lastly, given the population-level focus of the project, we aim to recruit approximately 6,125 people, and thus it would place great burden on participants to undergo a consent process for routinely collected data. All identifying information will be kept on secure UPHS servers and removed from all analytic datasets.

*Waiver of HIPAA authorization:*

For purposes of recruitment and linkage of survey data to EMR data, we are requesting a waiver of HIPAA authorization. This clinical trial meets the three criteria for a waiver of HIPAA authorization in accordance with the provisions for using protected health information (PHI) set forth in 45 CFR 46, § 164.512 (i) as follows: (1) the researchers require access to protected health information (PHI) in order to conduct the research, (2) The research cannot be practicably conducted without the waiver, and (3) the use or disclosure of PHI poses no more than minimal risk to participants. A request for Waiver of HIPAA form has been included in this protocol application.

**RESOURCES NECESSARY FOR HUMAN RESEARCH PROTECTION:**

The project is funded by an award from the National Cancer Institute. Our interdisciplinary team at the University of Pennsylvania includes investigators with distinguished records in implementation science, cancer care delivery, epidemiology, behavioral economics, pragmatic trials, EMR-based strategies, lung cancer screening, and mixed-methods research. The project will be led by [name], MSW, MPH, an interdisciplinary behavioral scientist specializing in cancer care delivery and implementation science research. Given the established clinical relationships with UPHS, we have access to necessary Epic data to identify patients and anticipate that research activities will be possible within the proposed timeline. Given the scope of the project and existing resources, we contend there is both sufficient time and adequate facilities to conduct the proposed research.

2. ABBREVIATIONS AND DEFINITIONS

| | |
|--------|--|
| AE | Adverse Event |
| EHR | Electronic Health Record |
| LCS | Lung Cancer Screening |
| LDCT | Low-Dose Computed Tomography |
| SAP | Statistical Analysis Plan |
| USPSTF | United States Preventive Services Task Force |

3. INTRODUCTION

a. Preface

Despite growing evidence that lung cancer screening (LCS) reduces lung cancer-specific mortality, LCS across the United States and at Penn Medicine is remarkably low (Fedewa et al. 2022). This is due in part to challenges with identifying adults who meet eligibility criteria for lifetime smoking intensity (i.e., 20 pack-years or greater), which is often missing from the electronic medical record. We developed a simplified tool (using yes/no questions) that has been shown to estimate pack-year eligibility accurately (Rendle et al. 2023). In this study, we aim to test the impact of different strategies (i.e., introductory and norming messages and incentives) on survey response rates when the survey is delivered via text message.

b. Scope of the analyses

These analyses will compare the effect of three different factors (introductory messages, norming messages, and incentives) on survey response rates using a 3x2x2 factorial design.

4. STUDY OBJECTIVES AND ENDPOINTS

a. Study Objectives

The primary objective of this analysis is to assess how the combination of different messaging content and incentives impact response rates to the survey.

b. Endpoints

The primary endpoint is full completion of the survey defined as responding to all three survey questions within 7 days of initial outreach. The secondary endpoint is partial completion of the survey (defined as responding to at least one survey question within 7 days of initial outreach).

5. STUDY METHODS

a. General Study Design and Plan

This single-blind study uses a 3x2x2 factorial design. Upon confirmation of their name, patients are randomized to one of the 12 potential study arms immediately based on two stratification variables (race and sex). If the patient does not confirm their name via text message, the patients will not be randomized nor included in the study. Upon randomization, the participants immediately receive the assigned interventions via text message.

| 3x2x2 Study Design | Tobacco Use Message A | | Tobacco Use Message B | |
|------------------------|-----------------------|--------------|-----------------------|--------------|
| | Incentive | No Incentive | Incentive | No Incentive |
| Introductory Message A | Arm 1 | Arm 2 | Arm 3 | Arm 4 |
| Introductory Message B | Arm 5 | Arm 6 | Arm 7 | Arm 8 |
| Introductory Message C | Arm 9 | Arm 10 | Arm 11 | Arm 12 |

b. Inclusion-Exclusion Criteria and General Study Population

Inclusion Criteria: Based on available EMR data at the time of enrollment, patients will be eligible if they:

- meet age eligibility (50-80 years old) for LCS based on 2021 USPSTF guidelines
- have completed at least one primary care visit at Penn Medicine in 2020-2025
- have a mobile phone listed in their medical record
- confirm identify at the time of initial outreach via text message.

Exclusion Criteria: Based on available EHR data at the time of enrollment, patients will be ineligible if they:

- have a documented history of lung cancer
- have a documented history of completing LCS at Penn Medicine
- are listed as not wanting to be contacted or solicited for research
- do not otherwise meet inclusion criteria.

c. Randomization and Blinding

Participants will be randomized into one of 12 study arms at the time of name confirmation. Randomization will occur using the randomization module within the Way-to-Health platform and be stratified by sex (female vs non-female) and race (Black adult vs non-Black adult). Single blinding (statistician) will be used in this study. Participants are randomized in blocks of 24 (12 study arms).

d. Study Assessments

Index date will be defined by the date that the participant is initially sent the first outreach text message (defined as the message that asks patients to confirm their name). At this point, the participant has seven days to respond to this text message, upon which they will be randomized immediately and given the assigned intervention. If they do not confirm their name or if they decline within 7 days, the patient will not be randomized or receive the intervention. For primary analysis, we will use the analysis time window below (7 days). To understand potential long-term reach, we will also assess the number of patients that responded after 7 days, including those who responded with name confirmation after 7 days and those who attempted to complete the survey after 7 days.

Primary and Exploratory Analysis Time Windows

| Days From Index Date | Lower bound (days) | Upper bound (days) |
|------------------------------|--------------------|--------------------|
| Day 0 (Primary Analysis) | 0 | 7 |
| Day 8 (Exploratory Analysis) | 8 | 60 |

6. SAMPLE SIZE

To determine the sample size for the trial, we considered a range of hypothesized response rates from 3% to 12% for the 12 arms representing different combinations of messaging and incentives and based on prior research studies. We hypothesized this range of response rates would be plausible for many of the arms and chose the final sample size based on our ability to distinguish statistically two arms towards the extremes of the range. Figure 1 below shows a plot of the 95% confidence intervals for the range of hypothesized response rates (plotted on both x- and left y-axes). With N=6,000 participants total (500 per arm), we would be able to detect a 5-percentage point difference between two arms if one of the arms had a response rate of 3% to approximately 7%. In comparison, with N=3,600 we would only be able to detect a 5-percentage point difference between two arms if one of the arms had a response rate of 3% or lower. Although larger samples would allow us to detect smaller differences, piloting on a larger sample would decrease the number of participants available for future trials. Balancing this logistical concern with power to detect differences between arms, we chose to include N=6,000 participants in this pilot study.

[figure not shown]

Figure 1: Illustration of 95% confidence interval length for potential response rates between 3% and 12%. Response rates are plotted on both the x- and y-axes. Each panel plots confidence intervals for the total sample size (N) given on the right y-axis.

7. GENERAL ANALYSIS CONSIDERATIONS

a. Timing of Analyses

The final analysis will be performed when at least 6,000 participants have randomized. The final analysis will be performed after all necessary cleaning and approval of statistician and after the finalization and approval of this SAP document.

b. Analysis Populations

i. Intention to Treat

All subjects who were randomized will be included in the intention to treat analysis. This will be the primary efficacy population for the purposes of the study.

ii. Per Protocol Population

All subjects who responded in any form (e.g., any text message response including but not limited to survey response) after receiving the intervention (i.e., after all interventions are delivered) will be included in the per protocol analysis. This will be the secondary efficacy population for the purposes of the study. This will exclude participants in the ITT that only confirmed their name and did not reply in any form after that.

c. Covariates and Subgroups

Covariates including baseline demographic (e.g., age, race, sex, ethnicity) and smoking history data (e.g., tobacco use status, lifetime smoking) will be extracted from the EHR. Variables used in randomization (sex and race) will be adjusted for in the primary analysis. We will assess baseline characteristics of each group by key covariates to assess any potential differences. Given persistent disparities in lung cancer by race and in LCS guidelines by race and sex, we will conduct exploratory subgroup analysis to assess potential treatment heterogeneity by race (Black adults vs Non-Black adults) and sex (female vs non-female). We do not hypothesize that our treatment will be different for each group, but given disparities, we conduct exploratory analysis to assess heterogeneity of treatment effects by race and sex.

d. Missing Data

The primary analysis model will adjust for race and sex. Since both these variables must be present in the EHR for randomization, there will be no individuals excluded due to missing race or sex in the analysis. There may however be participants in the dataset that have “unknown” race documented in the EHR. For randomization, these individuals are classified as “Non-Black” adults. For summary statistics, these individuals will be reported as unknown race. Due to the large number of patients to be randomized (N=500 per arm), we expect randomization to provide balance on all baseline covariates and therefore will not adjust for any other variables in the models. By definition, there will be no missing primary or secondary outcomes.

e. Multiple Testing

[figure not shown]
Since we are aiming to identify the best combination of factor levels, we are more concerned with making Type II errors than Type I errors. Therefore, we will not adjust for multiple testing.

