c. Protocol Deviations

We do not anticipate any major protocol deviations that could impact analysis, but one that would require adjustments would be if participants receive a different intervention than they are assigned to receive. This unlikely event might happen if there is an error in the programming code within WaytoHealth. Prior to analysis, we will review a subset of 50 randomly selected participants to review the content of all intervention messages received and assess concordance with their assigned study arm. If we identify that more than 5% received an incorrect intervention message, we will review all participants to ensure we have correctly classified them in the right intervention arm. After this, we will conduct subgroup analysis with and without misclassified participants to understand the impact on analysis and report our findings. Any misclassified participants might be excluded primary analysis depending upon subgroup analysis and reported as such.

d. Demographic and Baseline Variables

| Demographics and Baseline Variables | Source |
|---|--------|
| Age at index date | EHR |
| Race | EHR |
| Ethnicity | EHR |
| Sex | EHR |
| Sexual Orientation and Gender Identity | EHR |
| Socioeconomic Status (Based on Census-Tract) | EHR |
| Tobacco Use (Current, Former, Never, Unknown) | EHR |
| Pack-Years (Lifetime Smoking) | EHR |
| Other Smoking Data (E.g., Quit Date, Types) | EHR |

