9. EFFICACY ANALYSES

a. Primary Efficacy Analysis

All summary statistics will be produced in accordance with section 8, and all primary efficacy analyses will use the ITT population. All tests will be two-sided and use a Type I error of 0.05. First, we will test for a main effect of incentive versus no incentive using an independent proportions Z-test. If this main effect is significant, we will proceed to study the two messaging factors using only data from individuals randomized to the incentive condition with higher response rate. If the main effect of incentive is not significant, we will proceed with studying the two messaging factors using all data and assuming incentive level does not interact with messaging or have any other effect on the outcome. Next, using either half or all the data, we will model the binary indicator of complete survey response or non-complete survey response within 7 days using a logistic regression. The model will adjust for race and sex and will incorporate 5 indicators of treatment arm (3 introductory messaging levels x 2 tobacco use messaging levels – 1 reference group). We will compute the marginal response probability for each arm, averaging over the observed distribution of sex and race. Standard errors and 95% confidence intervals will be obtained for each marginal response probability using the delta method. If one of the confidence intervals has a lower limit that exceeds the upper limit of all the others, its corresponding set of factor levels will be used in the primary study, pending confirmation that exploratory analyses do not raise red flags about disparities in response rates. If a set of confidence intervals have lower limits that surpass the upper limits of the other intervals, the final choice of factor levels to use will be based on discussions amongst the study team and key stakeholder, taking into consideration the point estimate, confidence interval length, and exploratory data on disparities.

i. Secondary Analyses of Primary Efficacy Endpoint

We will conduct secondary analyses of the primary efficacy endpoint using the per protocol, instead of the ITT population, to assess if documented engagement after receipt of the full intervention affected efficacy.

ii. Analyses of Secondary Endpoints

We will conduct similar analysis outlined in Section 9a to assess the effect of the interventions on the secondary outcome, partial completion of the survey.

b. Exploratory Efficacy Analyses

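### The SAP gives expected balance as its reason for not adjusting for age and tobacco status, and its incentive test omits the sex and race adjustment that section 7c promises: a modest efficiency and consistency point

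*SAP*

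**What the plan says.** - **SAP 7c (Covariates and Subgroups):** "Variables used in randomization (sex and race) will be adjusted for in the primary analysis".
- **SAP 7d (Missing Data):** the primary analysis model adjusts for race and sex, and then "we expect randomization to provide balance on all baseline covariates and therefore will not adjust for any other variables in the models".
- **SAP 8d (Demographic and Baseline Variables):** age at index date is taken from the EHR, as is "Tobacco Use (Current, Former, Never, Unknown", so an unknown status is a recorded level and not a missing value.
- **SAP 9a (Primary Efficacy Analysis), first step:** "we will test for a main effect of incentive versus no incentive using an independent proportions Z-test". The result decides whether the message factors are studied in everyone or in one incentive condition only.
- **SAP 9a, second step:** a logistic model with race, sex and five arm indicators. It yields a marginal response probability per arm with a delta-method 95% interval. A combination is preferred when its interval clears the others.
- **SAP 6 (Sample Size):** "we considered a range of hypothesized response rates from 3% to 12% for the 12 arms", and the authors "chose the final sample size based on our ability to distinguish statistically two arms towards the extremes of the range".

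**The concern.** Two things stand out.

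1. **The reason given does not support the choice.** Balance protects against confounding. Adjusting for a covariate that predicts the outcome reduces residual variance even when the arms are perfectly balanced on it. SAP 7e says the team worries more about Type II than Type I error, and 9a chooses between combinations by whether intervals separate, so interval width bears directly on the decision. All three survey questions are about smoking, and the inclusion criteria do not require tobacco use, so recorded tobacco status could plausibly predict who answers. The same may be true of age.

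2. **Sections 7c and 9a do not agree.** The incentive test stands under the heading for the primary efficacy analysis and acts as its gate, but it adjusts for nothing.

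At stake is a little precision in the incentive decision and in separating message combinations, together with clarity about what the primary analysis adjusts for.

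**Working it through.** **Inputs from the SAP.** Section 9a: "All tests will be two-sided and use a Type I error of 0.05". Section 6: response rates of 3-12%, and "With N=6,000 participants total (500 per arm), we would be able to detect a 5-percentage point difference between two arms" if one arm's rate lies between 3% and about 7%; with N=3,600 (300 per arm) only at 3% or lower. Equal allocation to 12 arms puts about 3,000 people in each incentive condition. The documents give no association of age or tobacco status with response, so the inputs of that kind below are assumptions.

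**Step 1: the SAP's own sizing.** Two separate Wald 95% intervals for p and p + 0.05 do not overlap when

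1.96 × [√(p(1−p)/n) + √((p+0.05)(0.95−p)/n)] < 0.05.

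The largest p that satisfies this is 6.67% for n=500 and 3.00% for n=300. Both agree with section 6.

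**Step 2: what adjustment buys.** If the added covariates explain a share R² of outcome variance, the standard error of a marginal probability or risk difference is multiplied by √(1−R²). That is worth N·R²/(1−R²) extra participants. R² is Var(p_i)/[p̄(1−p̄)], where p_i is the response probability given the covariates.

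*Simple case inside the SAP's range.* Assume response of 12%, 8% and 4% in current, former and never smokers, with shares 15/25/60%.
- p̄ = 0.018 + 0.020 + 0.024 = 0.062.
- Variance = 0.15×0.058² + 0.25×0.018² + 0.60×0.022² = 0.000876.
- R² = 0.000876/(0.062×0.938) = 1.5%.
- SE reduction = 1 − √(1−0.015) ≈ 0.75%, worth about 92 participants on 6,000.

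*Age and tobacco together.* Assume standardized age truncated at ±1.7 SD and shares of 15% current, 30% former, 55% never or unknown. Odds ratios are per SD of age / current / former, relative to never.

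| Assumed strength | R² at 3% to 12% response | SE reduction | Equivalent extra N on 6,000 |
|---|---|---|---|
| Weak (1.2/1.5/1.25) | 0.1-0.5% | 0.1-0.2% | about 8-30 |
| Moderate (1.5/2/1.5) | 0.6-1.9% | 0.3-1.0% | about 34-118 |
| Strong (2/3/2) | 1.6-5.3% | 0.8-2.7% | about 100-338 |

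A different assumed mix (15/35/45/5%, the last unknown) with age values beyond ±1.7 SD set to that limit moves the upper ends only slightly, to 1.1% (moderate) and 3.1% (strong).

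**Step 3: effect on the plan's decisions.** Enter n/(1−R²) in the two-proportion power formula and in the Step 1 inequality.

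| R² | Power, 7% vs 12%, 500 per arm | Power, incentive 7.5% vs 9.5%, 3,000 per group | Highest lower-arm rate for interval separation |
|---|---|---|---|
| 0 | 77.0% | 79.3% | 6.67% |
| 1% | 77.4% | 79.7% | 6.76% |
| 5% | 79.1% | 81.3% | 7.18% |

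**Step 4: simulation of the incentive comparison.** N=6,000, stratified 1:1, 600 runs per scenario. Going from unadjusted to adjusted for sex, race, age and tobacco status, the empirical SE fell from 0.00671 to 0.00665 (7.6% response, moderate predictors) and from 0.00760 to 0.00742 (9.9%, strong). Adding only sex and race, with assumed odds ratios 1.2 and 0.8, made no measurable difference. With no true effect (8.9%, strong), the Z-test rejected in 5.7% of runs and the fully adjusted test in 6.0%. The Monte Carlo SE is √(0.05×0.95/600) = 0.9 points, so both are compatible with 5%.

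**Step 5: higher response.** Randomization follows name confirmation, so response among those randomized could exceed 12%. At assumed rates of 30-70%, the SE reduction would be about 2% (moderate) to 5% (strong).

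**The case against.** The strongest reply is that nothing is wrong. Adjusting only for the stratification factors is an accepted, pre-specified choice. It is unbiased under randomization and spares the team decisions about the functional form of age and about sparse tobacco levels. At 3-12% response the gain is too small to be likely to change which combination is chosen. Section 7d speaks of the primary analysis *model*, so the promise in 7c can be read as covering only the logistic step, and adding sex and race alone to the incentive test changes nothing measurable. **Most of this stands.** What remains is that the stated reason does not bear on precision, and that 9a lists the Z-test as part of the primary analysis, so 7c and 9a should be made to agree.

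Three stronger readings are tempting, and the documents support none of them.

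- A reader might infer that leaving out age and tobacco status makes the analysis biased or invalid. It does not: arms are randomized, and by 7d's definition no outcome is missing.
- A reader might say that precision is given up for no benefit. The plan does gain a simpler model.
- A reader might infer a loss worth many hundreds of participants. That needs response well above the SAP's planning range together with strong predictors, and the documents give neither. In the branch where only one incentive condition is analysed, the base for the message model is about 3,000 and not 6,000, which halves any participant equivalent.

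**Conclusion.** The point holds as a modest efficiency and consistency improvement to a valid analysis. At the planned response rates the SE reduction is roughly 0.1-1% for weak to moderate predictors and up to about 2.7% for strong ones. In power that is about 0.4 points at R² of 1% and about 2 points at R² of 5%. It would be larger only if name-confirmers respond at well above 12%. All these sizes depend on assumed associations, tobacco mix and age distribution. The mismatch between 7c and 9a does not depend on any assumption. Correcting it with sex and race alone would bring consistency but no measurable precision.

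**What to change.** 1. **Incentive step (9a).** Replace the Z-test with a separate logistic model fitted to all randomized participants, containing an incentive indicator, sex, race, age and four-level tobacco status. Test incentive as a standardized risk difference. A separate model is needed because the existing 9a model has no incentive term and is fitted afterwards, on data selected by the incentive result.
2. **Message-arm step (9a).** Add age and four-level tobacco status, with 'Unknown' as a level, to the existing logistic model. Keep the standardized marginal probabilities and delta-method intervals, so the quantity being estimated does not change.
3. **Section 7d.** Amend the sentence that excludes other variables so that it matches.

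**Cost.** This is more than a wording change, because step 1 adds a model, but it needs no new data and loses no participant for unknown tobacco status. The message-arm model becomes slightly larger: 5 arm + 1 race + 1 sex + 1 age + 3 tobacco = 11 coefficients besides the intercept. If only one incentive condition is used and response is near 3%, there are about 3,000 × 0.03 = 90 events, or about 8 per coefficient, which is thin. At 7.5% there would be about 225 events, or about 20 per coefficient. If the team prefers the simpler model, the minimum change is to reword 7c or 9a so that they agree on what the incentive test adjusts for.
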